-Due to power limitations we will restrict the number of covariates/independent variables to eight (10 patients/independent variable)(63). Based on suspected prognostic factors for LBP disability (61, 62) and suspected factors associated with serum cytokine levels (64, 65), we will add the following as covariates into the model due to possible confounding: age, leg pain (0-10 NRS), fear avoidance, emotional distress (dichotomized into HSCL-25 $\geq 1,75$ and $< 1,75$), psychiatric comorbidity (yes/no), other specific comorbidity (numerical, one point for each of rheumatoid arthritis, osteoarthritis, Diabetic, Cardiac/pulmonary) and sick leave (categorized into 1. working full time, 2. partial sick leave and 3. complete sick leave / disability pension / unemployed / student/other/unknown). Age, leg pain and fear avoidance will be continuous variables.

For each model we will evaluate:

1. The predictiveness by comparing the multiple correlation coefficient R^2 of the complete model with the R^2 in the model without the independent variable of interest (66).
2. The effect size described in terms of relative change in RMDQ. We will consider effect size $>30\%$ as clinically relevant, which equates approximately to a difference of 4 out of 12.8 (at baseline) RMDQ points.

The following models (1, 2A, 2B, 3, 4A, 4B, 5A, 5B, 5C, 5D, 5E) will differ in choice of independent variable of interest, which will be:

1. Cytokine category group based on cytokine classification group (4 categories of patients, figure 2). Each category of patients will be assessed versus the three other categories combined.
2. Classification variable defined by a Recursive Partitioning analysis using RPART command in R. Relative change in RMDQ from baseline to one-year follow-up will be dependent variable. Only patients nonmissing values in both baseline and one-year follow-up RMDQ score will be included. Stopping conditions will be $\text{maxdepth}=3$ and n_{min} (minimal number of observations in terminal/leaf node)=5. We will use tenfold cross-validation and a complexity parameter of 0,01. We will perform two Recursive Partitioning models that differs only in what variables that are included:

Statistical Analysis Plan for analysis of cytokines as prognostic factors and predictors of antibiotic treatment effect in patients with chronic low back pain and Modic changes (the AIM trial) - - version 1.0

- A. all 39 cytokines

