With 30% improvement of RMDQ from baseline to one-year follow-up as the gold standard status (diagnostic variable), we will calculate Area under ROC curve (AUC), cutoff value, positive predictive value, negative predictive value, sensitivity and specificity for each independent variable of main analyses (1, 2A and 2B) as a prognostic variable of interest (test variable). We will consider the same calculations for each independent variable of the additional analyses (3 to 5).

Assess the direct effect of cytokines on relative change in RMDQ score (baseline to 1-year) in the possible case that baseline value of RMDQ mediates any overall/total effect:

For each linear regression model of the main analyses (1, 2A and 2B) we will perform the same analysis including baseline value of RMDQ as a covariate. These models could also be interpreted to provide estimates of the prognostic effect (without causal inference) of cytokines given a specific baseline value, and we can therefore safely ignore the possible problems with bias mentioned above (under Main analyses). We will consider the same sensitivity analysis for each linear regression model of the main analyses (3 to 5).

Assess the effect of cytokines on relative change in RMDQ score (baseline to 1-year) in the placebo group only, in the possible case that that the subgroup predicts treatment effect:

We will consider (depending on results and power), for each linear regression model of the analyses 1, 4 and 5, performing the same analysis including only patients in the placebo group.

Internal validation

We will consider internal validation on any analyses 1 to 5 (depending on results) by using bootstrapping.

Sensitivity analyses:

The following sensitivity analyses will be performed for the main analyses (1, 2A and 2B), and will be considered performed for the main analyses 3 to 5:

Assess the possibility that covariates included in main analyses are non-confounders/mediators:

For each linear regression model of the main analyses 1, 2A and 2B, we will perform unadjusted analysis with relative change in RMDQ from baseline to one-year follow-up as dependent variable, and the same independent variable as used in each respective model (1, 2A and 2B). These unadjusted analyses are recommended as we cannot rule out the possibility that the covariates included in the main analyses could be non-confounders or mediators (72). Each model will be compared to their respective main analysis by assessing R^2 .

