Assess other possible confounders (not included in main analyses due to power limitations):

We will perform a sensitivity analysis for the main analysis (1, 2A and 2B), with the same statistical model but only including covariates with statistically significant beta coefficient in the corresponding main analysis, and depending on available number of further covariates (given maximum eight), the

Statistical Analysis Plan for analysis of cytokines as prognostic factors and predictors of antibiotic treatment effect in patients with chronic low back pain and Modic changes (the AIM trial) - - version 1.0

following covariates will be considered: treatment group (amoxicillin/placebo), comorbidity, NSAIDs use (at baseline and one-year follow-up), physical workload, sleep disturbance(64), BMI, smoking, LBP intensity at baseline (0-10 NRS), and prior surgery for disc herniation. Each sensitivity analysis will be compared to their respective main analysis by assessing R^2 .

The following sensitivity analyses will be considered performed:

Assess the possibility of non-linear effects of the cytokine

For each main analyses 5 (A-E), we will consider using a correspondent multivariable fractional polynomial (MFP) model or other polynomial regression model (73). All covariates of the original regression analyses will be forced included (by setting nominal p-values for variable selection to one in MFP model), only the independent variable of interest will be tested for a non-linear relationship (degrees of freedom for other continuous variables will be set to one) with (for MFP) standard powers (-2, -1, -0.5, 0, 0.5, 1, 2, and 3) and a fractional polynomial election significance level of 5% (using the mfp command in Stata). Each MFP model will be compared to its respective main analysis by assessing R^2 .

Independence of effect:

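### Hypothesis 2 analyses that change the covariate set are compared with the main analysis only on R², which does not show whether the cytokine association changes

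*SAP*

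**What the plan says.** All references are to the SAP section on cytokines as prognostic factors (hypothesis 2).

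- **Main analyses.** Each model is judged on two things. The first is the R² of the complete model against the R² "in the model without the independent variable of interest". The second is the effect size in relative RMDQ change, with more than 30% taken as clinically relevant.
- **Sensitivity analysis on non-confounders and mediators.** Unadjusted models are fitted for main analyses 1, 2A and 2B. The reason given is that "we cannot rule out the possibility that the covariates included in the main analyses could be non-confounders or mediators". The comparison rule is: "Each model will be compared to their respective main analysis by assessing" R².
- **Sensitivity analysis on other possible confounders.** The models for 1, 2A and 2B are refitted "only including covariates with statistically significant beta coefficient in the corresponding main analysis", then filled up from a further list to a maximum of eight. The rule is: "Each sensitivity analysis will be compared to their respective main analysis by assessing" R².

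Neither sensitivity analysis names a comparison of the cytokine coefficient or its confidence interval. The two main-analysis criteria are not expressly carried over to them.

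**The concern.** Both analyses ask whether the association between the cytokine variable and outcome depends on which covariates are in the model. The answer lies in that variable's coefficient and its interval. Whole-model R² describes how well all terms together fit the outcome, and it is dominated by whichever covariates are prognostic.

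A covariate can raise R² greatly and leave the cytokine coefficient untouched. It can also raise R² by the same amount and remove the coefficient altogether. If the report follows the stated rule literally, a reader sees a large fall in R² in the unadjusted model and learns nothing about robustness. That fall could be mistaken for evidence that the covariates matter as confounders, or an R² that hardly moves in the other-confounders analysis could be mistaken for evidence that they do not.

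**Working it through.** **Inputs from the SAP (power paragraph for hypothesis 2).** n = 78; R² = 30% with seven covariates and no cytokine variable; detectable increase 7 percentage points at α = 0.05 and β = 0.2.

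**Step 1: the plan's own figure.** F test for an R² increment with one tested variable: df = 1 and 78 − 7 − 1 − 1 = 69; noncentrality = n × Δ / (1 − R² of the full model) = 78 × 0.07 / (1 − 0.37) = 8.67. Power is 0.827. The increment giving exactly 80% power is 6.6 points, which rounds to the stated 7. The SAP's figure is reproduced.

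**Step 2: unadjusted against main, algebra.** The outcome and the variable of interest are the same and only covariates are removed, so the models are nested. Least squares cannot fit worse with more terms, so on the same patients R²(unadjusted) ≤ R²(main) always. Two constructed cases, with standardised variables:

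- *No confounding.* The cytokine is independent of the covariates. R² is 0.07 unadjusted and 0.30 + 0.07 = 0.37 in the main model. The coefficient is √0.07 = 0.26 in both.
- *Complete confounding.* The cytokine has no effect of its own and the covariates explain 0.37. The cytokine correlates √(0.07/0.37) with the covariate score, so its squared correlation with outcome is (0.07/0.37) × 0.37 = 0.07. R² is again 0.07 and 0.37. The coefficient is 0.26 unadjusted and 0 adjusted.

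The R² pair is the same in both cases, while the coefficient separates them.

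**Step 3: the same at n = 78.** 4000 simulated data sets per case; independent normal covariates assumed. Sample R² lies above the population value because of the number of fitted terms.

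| Case | Mean R² unadjusted | Mean R² main | Coefficient unadjusted | Coefficient main |
|---|---|---|---|---|
| No confounding | 0.078 | 0.430 | 0.261 | 0.262 |
| Complete confounding | 0.079 | 0.430 | 0.263 | −0.002 |
| Seven pure-noise covariates | 0.080 | 0.164 | 0.263 | 0.263 |

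R² was higher in the main model in 100% of data sets in every case, including the one where the covariates were noise.

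**Step 4: other possible confounders.** Covariates are both dropped and added, so the models are in general not nested and the direction of R² is not fixed. When five noise covariates were swapped for five others, mean R² was 0.431 in both models, and the sensitivity model had the higher value in 50% of data sets. A change in either direction does not show what happened to the cytokine coefficient.

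**Step 5: incremental R².** In a separate simulation of the first two cases, the cytokine's own R² was 0.078 (no confounding) and 0.080 (complete confounding) when unadjusted. Its increment in the main model was 0.070 and 0.008. The increment therefore does discriminate, unlike whole-model R².

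**The case against.** The best defence is that objective 2 concerns added prognostic value, for which R² is a natural measure, and that the main-analysis section defines its use as an increment for the variable of interest. On that reading the comparison is informative, as Step 5 shows. It stands that R² belongs in this plan. But the sensitivity sections speak of comparing one model with another and do not mention the increment, so the favourable reading has to be supplied by the reader.

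It is also fair that the main models are judged on effect size and that the sensitivity models will produce coefficients anyway. That makes the repair easy, but the stated comparison still leaves the coefficient out.

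Three stronger readings are tempting and are not supported:

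- *That R² moves by construction in every comparison.* This is strictly true only of unadjusted against main.
- *That non-linearity is also judged by R² alone.* The SAP does say "Each MFP model will be compared to its respective main analysis by assessing" R², but the analysis is optional ("we will consider using a correspondent multivariable fractional polynomial (MFP) model or other polynomial regression model") and carries a 5% selection level under which "only the independent variable of interest will be tested for a non-linear relationship". Main models 5A–E use categorised cytokines, so that comparison is not nested either, and polynomial terms need not raise R².
- *That all handling of mediation rests on R².* The supportive analysis that adds baseline RMDQ as a possible mediator states no R² comparison.

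Finally, a shift in the coefficient looks the same under confounding and under mediation. The better metric shows whether the association changes; it does not show why.

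**Conclusion.** The point holds for the two analyses that change the covariate set, applied to main analyses 1, 2A and 2B. Under the literal rule, an unchanged cytokine effect and a vanished one give practically the same R² comparison (about 0.08 against 0.43). The direction of the nested result is algebraic and needs only that both models use the same patients. The sizes rest on the SAP's 30% and 7% and on assumed independent normal covariates with either no confounding or complete confounding; real data will lie between these.

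Severity is minor. The SAP declares all its analyses exploratory, these are sensitivity analyses, and no main conclusion depends on the R² sentences.

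**What to change.** In the two sensitivity sections (non-confounders and mediators; other possible confounders), replace the R² comparison with:

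1. The coefficient of the cytokine variable, as its effect on relative RMDQ change, is reported with its 95% CI side by side for the main and sensitivity models.
2. The incremental R² of the cytokine variable, defined as in the main analyses, is reported for each model.
3. Whole-model R² is given as description only.
4. A change in the coefficient is not taken by itself to distinguish confounding from mediation.

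The cost is a few sentences. The coefficients come from models already planned; the increment needs one further fit per sensitivity model, without the cytokine variable. For the unadjusted model, the increment is simply its R².
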